6.5 Amputation and Peripheral Revascularization

Amputation is defined as non-traumatic amputation of an extremity more proximal than the distal phalanx.

Peripheral revascularization is defined as revascularization of any peripheral artery either surgically or percutaneously.

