9.2 Statistical Analysis

The analyses will examine the effects of long-term evolocumab therapy on cardiovascular events, total mortality, and cause-specific mortality. Analyses will include all participants who entered the FOURIER LEGACY study in participating countries, irrespective of whether they completed the FOURIER LEGACY study. (Data including baseline characteristics, medications, event history and during follow-up etc. will be incorporated into the follow-up database from the FOURIER OUTCOMES trial database). The characteristics of participants at participating sites/countries who did and did not contribute to the FOURIER LEGACY study will be compared. Likewise, the characteristics of subjects who complete the FOURIER LEGACY study vs. those who do not will be compared.

Qualitative and quantitative data will be described using counts, means, medians, and percentages with ranges or standard deviations as appropriate. Event data will be analyzed according to the participants' original randomly assigned therapy in the OUTCOMES study, on an intention-to-treat basis. Time to event information will be presented using Kaplan-Meier curves, and described according to Cox proportional hazard ratios (and 95% CIs), with comparisons between curves using standard log-rank tests. Similar methodology will be used for analyses of any pre-specified subgroups (e.g., baseline participant characteristics). In the circumstance that the hazards violate the test of proportionality, methods such as time-partitioned regression techniques will be utilized. Tests for interaction will be used to evaluate for evidence of differences in treatment effects between subgroups. Recurrent event analysis will be performed using the methods of Wei, Lin and Weissfeld¹². Analyses, both unadjusted and adjusted for baseline measures, will be performed. Cause-specific mortality will also be analyzed using competing risks methods.

Further analysis investigating the impact of baseline characteristics (at time of randomization into the OUTCOMES study) on events will be performed using regression methods (linear, logistic, and proportional hazards) as appropriate.

Separate analyses examining effects post study close will be performed to evaluate the trajectory of effects long-term using appropriate methods (e.g., landmark analysis and conditional probability plots), again by original treatment assignment, among the FOURIER LEGACY study cohort from the time of randomization.

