14 APPENDICES

14.1 Appendix 1. Questionnaire to Patients

Since you last made contact with us, have you suffered from any of the following new health events?

- (i) A new heart attack? (Y/N/Unsure)
- (ii) A new stroke? (Y/N/Unsure)
- (iii) Had one or more new coronary angioplasties (balloon treatment) or coronary stenting? (Y/N/Unsure)
- (iv) Had new coronary artery bypass surgery? (Y/N/Unsure)
- (v) Had a new angioplasty (balloon treatment) or stenting to the leg vessels? (Y/N/Unsure)
- (vi) Had an amputation of any limb (not relating to injury or accident)? (Y/N/Unsure)
- (vii) Been admitted to hospital for your heart condition (cardiovascular hospitalization is defined as hospitalization for any cardiovascular (heart or blood vessel) reason)? (Y/N/Unsure)

[For each of the above, if yes, please give month and year]

[If response is "unsure", then "thank you, we will contact you directly to help clarify your answer"]

Please also answer the following questions:

- (viii) Are you still taking a statin tablet to lower your cholesterol (you needed to be taking one to take part in the FOURIER trial)? (Y/N/Unsure)
- (ix) Are you still taking a cholesterol lowering injection (PCSK9 inhibitor drug) similar to as in the FOURIER trial (you needed to start one when you joined the FOURIER trial)? (Y/N/Unsure)
- (x) Are you taking a medication (e.g., ezetimibe or Zetia) to slow absorption of cholesterol from your diet? (Y/N/Unsure)

PLEASE INDICATE BELOW IF YOU WISH TO BE CONTACTED BY THE STUDY TEAM TO DISCUSS ANY NEW HEALTH ISSUES SINCE WE LAST CONTACTED YOU (Y/N)

Thank you very much for your participation, and for keeping us updated about your health. We will contact you again in 1 years' time to stay in touch. If you have told us that you have had one of the above health events, then we may contact you sooner, to learn more about it if necessary.

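### Questionnaire item (v) is narrower than the Section 6.5 definition of peripheral revascularization, item (vi) is ambiguous for toe and part-foot amputations, and repeat events have no explicit count or dates

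*Protocol*

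**What the plan says.** Protocol Section 6.5 sets the two definitions: "Peripheral revascularization is defined as revascularization of any peripheral artery either surgically or percutaneously" and "Amputation is defined as non-traumatic amputation of an extremity more proximal than the distal phalanx". Together they form the fifth secondary objective in Section 2, and Section 5.1 schedules them at every contact.

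Section 5.2 refers to Appendix 1 (Section 14.1) for what is collected. There, item (v) reads "Had a new angioplasty (balloon treatment) or stenting to the leg vessels" and item (vi) reads "Had an amputation of any limb (not relating to injury or accident", closing its bracket at that point. Item (iii), for coronary procedures, reads "Had one or more new coronary angioplasties (balloon treatment) or coronary stenting". The items share the opening "Since you last made contact with us, have you suffered from any of the following new health events" and the bracketed instruction "For each of the above, if yes, please give month and year".

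For the analysis, Section 9.2 states "Recurrent event analysis will be performed using the methods of Wei, Lin and Weissfeld".

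**The concern.** Appendix 1 is the main route by which non-fatal events reach the database. An endpoint defined more broadly than the question that feeds it will tend to be under-counted, and no analysis plan can restore events that were never asked about. Here the question leaves out a type of procedure (open surgery) and a set of sites (arteries outside the leg), both of which the definition includes.

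Two lesser problems sit beside it. A lay reader may not think of a toe as a limb. And a Wei-Lin-Weissfeld analysis models the time to the first, second and later events, so it needs a date for each, while the form does not explicitly ask how many events occurred or for each date.

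At stake are the absolute rates and the precision of one secondary objective, and the completeness of the recurrent-event analysis.

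**Working it through.** **The plan's own figures.** The protocol gives no rate, power or loss for peripheral events, so there is none to reproduce on this point. For context, the Section 9.1 power figures hold up. With 5,000 per arm (1:1 assumed), a control rate of 5% per annum and 5 years, a hazard ratio of 0.80 gives 5,000 × [(1 − e^−0.25) + (1 − e^−0.20)] ≈ 2,012 events and 99.9% power (stated: over 95%). A hazard ratio of 0.85 gives about 2,063 events and 95.8% (stated: over 90%). The point does not depend on them.

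**Definition against question.**

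| Event | Section 6.5 | Appendix 1 |
|---|---|---|
| Balloon or stent, leg artery | counted | asked, item (v) |
| Bypass or other open surgery, leg artery | counted | no specific item |
| Any procedure on a peripheral artery outside the leg | counted | no specific item |
| Major limb amputation, non-traumatic | counted | asked, item (vi) |
| Toe or part-foot amputation above the distal phalanx | counted | ambiguous, item (vi) |

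For the coronary arteries the form asks about bypass surgery separately, in item (iv). There is no peripheral counterpart.

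**Effect of incomplete capture (illustration only).** If a net share m of qualifying events is never recovered, the observed rate falls by m and the standard error of the log hazard ratio rises by 1/√(1 − m). Assume, with no support in the documents, a 5-year control rate of 3% and a hazard ratio of 0.80. Full capture then gives 5,000 × (0.03 + 0.024) = 270 events. Power is Φ(√D/2 × |ln 0.80| − 1.96), where D is the number of captured events.

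| Captured | Events | SE factor | Power |
|---|---|---|---|
| 100% | 270 | 1.00 | 45% |
| 80% | 216 | 1.12 | 37% |
| 60% | 162 | 1.29 | 30% |
| 40% | 108 | 1.58 | 21% |

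**Repeat events.** If only one date is entered per item per interval, and events follow a Poisson process with rate λ over an interval of T years, the share of events lost is 1 − (1 − e^(−λT))/(λT). The rates below are assumed.

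| λT | Share lost |
|---|---|
| 0.05 | 2.5% |
| 0.10 | 4.8% |
| 0.20 | 9.4% |

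For annual contacts T = 1. The entry questionnaire looks back to the last contact in the parent trial, a gap whose length is not stated. If it were 2 years, a rate of 0.10 per year would give λT = 0.20 and a 9.4% loss. Repeat procedures tend to cluster in the same patients, which the Poisson model ignores, so the true share could be higher.

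**The case against.** The strongest case against is that the form has other routes. Item (vii) asks about admission for any heart or blood-vessel reason, so a peripheral operation in hospital should give a dated Yes. An Unsure answer brings direct contact. Every participant can ask to be contacted. Section 3.2 provides signed authorization to seek source documents, and Section 5.2 allows registry data where local rules permit.

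This stands in part. A reader might infer that the unlisted procedures are simply missed; the documents do not support that. But item (vii) opens with the heart condition and mentions blood vessels only inside a bracket, and a Yes there records an admission, not a procedure. Contact after a reported event is optional. Adjudication under Section 8.1 covers at least 10% of non-fatal cardiovascular events and acts on events already reported. None of these routes is directed at the unlisted procedures, so the gap is narrowed, not closed.

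Three further limits stand in full:

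- A reader might take item (vi) to exclude toes. It does not; limb and extremity are close in meaning, and a doubtful patient can answer Unsure. The problem is ambiguity.
- A reader might conclude that second events are lost in general. Repeats in different contact intervals, or under different items, can each be dated. That only one date can be entered is itself an inference from a bracketed instruction, since the web form is not shown.
- A reader might infer a biased hazard ratio. If reporting does not depend on original allocation, loss should be similar between arms, and the cost is in rates and precision.

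**Conclusion.** The mismatch between item (v) and Section 6.5 is plain on the page and should be corrected. The ambiguity in item (vi) and the absence of an explicit count and date for each event are smaller faults, worth mending in the same amendment.

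The likely consequence is understated absolute rates and reduced precision for the amputation and peripheral revascularization objective, plus some loss of same-item repeats in the recurrent-event analysis. The size cannot be fixed from the documents: every capture share, the 3% event rate and the repeat rates used above are assumptions. The conclusion that the comparison between arms is not materially biased rests on reporting being unrelated to original allocation.

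The first-event primary analysis is essentially unaffected. Items (i) to (iv) cover its non-fatal components, including both catheter and surgical coronary procedures.

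**What to change.** Amend Appendix 1 as follows.

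- **Item (v):** ask about a balloon, stent or surgical procedure on any peripheral artery within the Section 6.5 definition. Which arteries count should follow the adjudication guidelines, which are not shown here.
- **Item (vi):** name toe, part of the foot, finger and hand, keep the exclusion of injury, and let the national co-ordinating center apply the Section 6.5 threshold.
- **Every event item:** ask for the month and year of each event since the last contact.
- **Recovery of earlier events:** at the next contact, ask the reworded items (v) and (vi) once for the whole period back to parent-trial close-out. Flag those answers, because the recall period is longer than at routine contacts.

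The cost is one questionnaire amendment, with the ethics approval that Section 11.3 requires before implementation across the participating countries, and a slightly longer form. Section 12 shows that questionnaire changes were already made in versions 1.2 and 1.3.

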Secondary objectives	
2. To evaluate the long-term effect of evolocumab treatment on CV death, MI and stroke.3. To evaluate the long-term effect of evolocumab treatment on CV death.4. To evaluate the long-term effects of evolocumab treatment on CHD death.5. To evaluate the long-term effect of evolocumab treatment on the individual components of the primary endpoint and any other CV hospitalizations.6. To evaluate the long-term effect of evolocumab treatment on amputations and peripheral revascularization.7. To evaluate the long-term effect of evolocumab treatment in terms of all-cause death (and non-CV, including cancer, death).
Exploratory objective	
8. To assess the effect of use of lipid-lowering treatment classes (statins, cholesterol absorption inhibitors, PCSK9i).9. To assess the effect modification by baseline characteristics on defined study outcomes above.
Design	
International multi-center observational, longitudinal follow-up study of participants who participated in the FOURIER OUTCOMES trial.

Population	
Participants in selected countries who completed the FOURIER OUTCOMES trial.

Study treatments	
None.

Assessments	
Participants will be remotely assessed (via questionnaire) upon entry into the FOURIER LEGACY study, approximately 6 and 12 months later and

[figure not shown]
then approximately annually to obtain a total of 5 years' follow-up after the date of last contact in the FOURIER OUTCOMES trial to collect details of cardiovascular hospitalizations, mortality and lipid-lowering therapy classes.

Statistical considerations

A minimum of 10,000 participants, followed over 5 years post-trial, with an assumed average post-trial event rate of 5% per annum for the primary endpoint, would have over 95% power at $2P=0.05$ to detect a 20% proportional event reduction accruing post-trial. It will also offer 80% power at $2P=0.05$ to detect a 23% reduction in CVD (from 4.94% to 3.8%).

Interim analyses of accrued data may be conducted annually post-trial as agreed from time to time by the study Steering Committee and funder. Analyses will be by intention-to-treat based on original allocated treatment in the parent FOURIER OUTCOMES trial.

Study Schema

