2 AIM AND OBJECTIVES

The aim of this study is to determine potential long-term effects on cardiovascular outcomes of evolocumab treatment in patients enrolled in the FOURIER OUTCOMES trial through extended follow-up of selected participants beyond the treatment period.

The **primary objective** is to evaluate potential long-term effects of evolocumab treatment on a composite of CV death, MI, stroke or coronary revascularization in patients completing participation in the FOURIER OUTCOMES trial over a period of up to 5 years following completion of the FOURIER OUTCOMES trial.

The **secondary objectives**, each over a period of up to 5 years following completion of the FOURIER OUTCOMES trial, are:

1. To evaluate the long-term effect of evolocumab treatment on CV death, MI and stroke.
2. To evaluate the long-term effect of evolocumab treatment on CV death.
3. To evaluate the long-term effect of evolocumab on CHD death.
4. To evaluate the long-term effect of evolocumab treatment on the individual components of the primary endpoint and any other cardiovascular hospitalizations.
5. To evaluate the long-term effect of evolocumab treatment on amputation and peripheral revascularization.
6. To evaluate the long-term effect of evolocumab treatment in terms of all-cause death (and non-CV, including cancer, death).

Two exploratory analyses will be performed:

1. To assess effect modification of use of prescription lipid-lowering treatment classes (statins, cholesterol absorption inhibitors, PCSK9i) administered at FOURIER OUTCOMES trial entry on the outcomes above.
2. To assess the effect modification by baseline characteristics on defined study outcomes above.

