5 ASSESSMENT PLAN

5.1 Schedule of Assessments

	Study entry, 6 and 12 months later and then annually to a total of 5 years post-end of FOURIER OUTCOMES trial
MI	X
Stroke	X
Coronary revascularization	X
Other CV hospitalization	X
CV death	X
CHD death	X
Amputation/peripheral revascularization	X
Non-CV death	X
Lipid-lowering therapies	X
Any adverse drug reactions from evolocumab treatment	X

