6.4 Cardiovascular Hospitalization

Cardiovascular hospitalization is defined as hospitalization for any cardiovascular reason.

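### The secondary objective concerns *other* cardiovascular hospitalization, but Section 6.4 and questionnaire item (vii) capture *any* cardiovascular admission without its reason, so the two can only partly be separated

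*Protocol*

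**What the plan says.** Three places in the Protocol name the endpoint as cardiovascular hospitalization *other* than events counted elsewhere:

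- Section 2, secondary objective 4: "individual components of the primary endpoint and any other cardiovascular hospitalizations".
- Synopsis, secondary objectives: "individual components of the primary endpoint and any other CV hospitalizations".
- Section 5.1, schedule: a row "Other CV hospitalization", apart from the rows for MI, stroke, coronary revascularization and amputation/peripheral revascularization.

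Two places use a wider term:

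- Section 6.4: "Cardiovascular hospitalization is defined as hospitalization for any cardiovascular reason".
- Appendix 1, item (vii), which begins "Been admitted to hospital for your heart condition (cardiovascular hospitalization is defined" and ends "hospitalization for any cardiovascular (heart or blood vessel) reason)? (Y/N/Unsure".

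The detail requested after a positive answer is the same for items (i) to (vii): "For each of the above, if yes, please give month and year". No item asks why the participant was admitted. If an event is reported, the closing paragraph says "then we may contact you sooner, to learn more about it if necessary".

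**The concern.** *Other* and *any* are different endpoints. An admission for MI, stroke, angioplasty or bypass surgery belongs under items (i) to (iv), and item (vii) as worded also calls for a yes. Nothing on the form tells the participant to leave out what was just reported.

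The objective sets other admissions beside the primary components, so a reader of the results will take a difference there as information additional to those components. If the data contain re-reported primary events, an effect on the components partly reappears under the second label, and any effect on truly other admissions is blended with it. Because the form never asks the reason, a later analysis rule cannot supply it.

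**Working it through.** **No stated figure is in dispute.** As a check that the sample size is untouched, I took 5,000 per arm (1:1 assumed), 5% per annum exponential over 5 years and a two-sided 5% level. Control risk is 1 − exp(−0.25) = 22.1%.

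- 20% reduction: treated risk 1 − exp(−0.20) = 18.1%, about 2,012 events, power 99.9%.
- 15% reduction: about 2,063 events, power 95.8%.
- CVD death 4.94% against 3.8%: power 79.6%.

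These agree with the over 95%, over 90% and 80% in Section 9.1.

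**How the form treats an admission**

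| Admission | Items (i)–(vi) | Item (vii) as worded | Meant by objective 4? |
|---|---|---|---|
| MI, stroke, coronary revascularization | yes, in (i)–(iv) | yes | no, already a component |
| Leg revascularization, vascular amputation | yes, in (v)–(vi) | yes | not stated; a separate objective |
| Any other cardiovascular reason | no | yes | yes |

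**What month matching can do.** Items (i) to (vii) are all dated by month and year, so an entry under (vii) that shares its month with a reported component can be dropped. Three gaps remain:

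1. A separate admission in the same month would be dropped with it.
2. Item (iii) covers one or more procedures. A second procedure dated to another month under (vii) may match nothing and would then count as other.
3. Item (vii) is one yes/no per contact, and contacts are about a year apart for most of follow-up. A participant who dates it to the MI admission may leave a later admission unrecorded. The form does not forbid several dates, but it does not ask for them.

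**Illustrative size**

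Inputs:

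- Primary endpoint rate: 5% per annum (Section 9.1).
- CVD death: 4.94% over up to 5 years (Section 9.1), so 4.94/5 ≈ 1% per annum.
- Non-fatal primary events: 5% − 1% ≈ 4% per annum.
- Assumed, not in the documents: truly other admissions at 2%, 3% or 5% per annum with no treatment effect; every non-fatal primary event is an admission re-reported under (vii); no date matching.

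Share of control-arm admissions that are primary events = 4/(4 + r). Apparent reduction = 20% × share.

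| r (% per annum) | Share | Apparent reduction | Hazard ratio (r + 4 × 0.8)/(r + 4) |
|---|---|---|---|
| 2 | 4/6 = 67% | 13% | 5.2/6 = 0.87 |
| 3 | 4/7 = 57% | 11% | 6.2/7 = 0.89 |
| 5 | 4/9 = 44% | 9% | 8.2/9 = 0.91 |

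The 4% treats every CV death as a first event, which makes it slightly low. At the other extreme (5%), the shares are 5/7 = 71% and 5/10 = 50%, and the apparent reduction is 14% to 10%, so the picture hardly changes.

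**The case against.** The strongest reply is that Section 6.4 defines only the base term and that the objective and schedule add the qualifier. Read together, the endpoint is a cardiovascular hospitalization not already counted as a component, and deriving it is a matter for the SAP, which is not shown. This stands as a reading of intent, and an SAP rule for matching by month would remove part of the overlap. It does not settle the matter, because no analysis rule can restore a reason that was never asked for.

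There are other routes to the reason: signed authorization to seek source documents (Section 3.2), registries where permitted (Section 5.2), source data for at least 10% of non-fatal CV events (Section 8.1) and follow-up contact when judged necessary (Appendix 1). These are real, and the 10% is a floor. All are partial or discretionary. The call-back for unsure answers does not help, because the truthful answer after an MI admission is yes.

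A reader might infer three stronger things that the documents do not support:

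- That the endpoint simply re-counts the primary events and cannot answer its objective. Nothing says the analyst will ignore the word *other*, and month matching is possible.
- That 9–13% estimates the bias. It is a worst case on rates that the documents do not give.
- That losing heart-failure or unstable-angina admissions as identifiable categories defeats an objective. No objective asks for them separately.

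**Conclusion.** The point holds in a limited form. The objective and schedule concern *other* cardiovascular hospitalization, whereas Section 6.4 and item (vii) capture any such hospitalization without a reason. Admissions for primary components therefore also count under (vii), month matching separates them only in part, and an effect on those components could partly carry over.

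One part of one secondary objective is affected. The primary endpoint, its components and the sample size are not.

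The size cannot be known from the documents. The 9–13% is an upper figure for a 20% reduction confined to primary events. It depends on other admissions at 2–5% per annum, complete re-reporting of about 4% per annum, and no matching. With matching, or with less than complete re-reporting, it would be smaller.

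**What to change.** 1. In Section 6.4, define other CV hospitalization as hospitalization for a cardiovascular reason, excluding any admission already counted as MI, stroke or coronary revascularization. State whether admissions for peripheral revascularization and amputation are also excluded. They are not primary components and have their own objective, so this is a choice for the sponsor to make explicit.
2. Reword item (vii) along these lines: *Apart from the events you reported above, have you been admitted to hospital for any other heart or blood vessel reason? If yes, please give the main reason, month and year of each admission.*
3. For answers already collected, remove entries that match a reported component by month, and state that limitation when reporting.

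The cost is one definition and one question by amendment (item (vii) was already amended in version 1.2, per Section 12), a slightly longer form, and two versions of the item across follow-up, which the analysis must acknowledge.

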The FOURIER OUTCOMES trial was a randomized double-blind placebo-controlled trial that demonstrated significant clinical benefits, with a 15% reduction in the composite endpoint of CVD death, MI, stroke, UAP or urgent revascularization over a median of 2.2 years follow-up, and a 20% reduction in CVD death, MI, and stroke, with no excess of any important adverse events.^{9,10} However, while beneficial over just a few years, these treatments will be designed for long-term use, such that high confidence in the value of the therapy can be better established with longer-term efficacy and safety data related to the treatment received during the FOURIER OUTCOMES trial.

The ODYSSEY OUTCOMES trial showed that among patients who had a previous acute coronary syndrome (ACS) and who were receiving high-intensity statin therapy, the risk of recurrent ischemic cardiovascular events was lower among those who received alirocumab than among those who received placebo.¹¹

We hypothesize that, in this observational study of participants who had taken part in the FOURIER OUTCOMES trial, prior use of evolocumab compared with placebo during the randomized FOURIER OUTCOMES trial, irrespective of post-trial treatment with or without further evolocumab, will confer additional effects post-trial on cardiovascular events and mortality beyond those observed at the end of the randomized study period; and that this will occur without any adverse signal on non-cardiovascular mortality.

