4.1 Concomitant Medication Reporting

Use of concomitant medications is solely at the discretion of participants and their treating physicians, including any lipid-modifying medication (including PCSK9 inhibitors). Use of lipid-modifying therapy classes will be recorded.

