5.2 Details of Assessments

Participants will be contacted upon entry into the FOURIER LEGACY study, and then approximately 6 months later. Following this, contact will be made approximately annually to obtain follow-up for a total of 5 years after the date of last contact in the FOURIER OUTCOMES trial. Each participant will be sent a unique link to a secure website and asked to provide details of any cardiovascular events and lipid-lowering therapy classes used since the last contact (Appendix 1 lists data to be collected). A proportion of events will be adjudicated as detailed in Section 8.1.

Participants will be contacted directly (by their preferred method of communication) or via a proxy, as agreed and in accordance with local regulations.

Participants who do not complete the required information despite reminders will be contacted directly by the relevant NCC.

Where permitted by local regulations, permission will be sought to collect data from any available national/local registries.

All consenting participants are expected to be followed up to the end of the study. All efforts must be made to maintain follow-up per the visit schedule. If this is not possible, follow-up should still occur wherever possible via periodic contact, the participant's other nominated contacts, their usual doctors, contact at study closure and any available national/local registries, as permitted by local regulations.

To ensure no bias is introduced into the assessment of possible late safety signals from prior evolocumab treatment in the FOURIER OUTCOMES trial, every effort will be made to ascertain causes of death for participants who may have died since the FOURIER OUTCOMES trial close-out and prior to the commencement of this study.

5.3 *Withdrawal From Contact or From Follow-up*

Withdrawal from on-going contact by the designated NCC may occur at any time by participant request, with confirmation to be documented clearly. Withdrawal of consent should only occur if the participant refuses any further assessments or contact whatsoever. Any data collected prior to a participant's withdrawal of consent will be maintained in the database and analyzed.

It is expected that all options for continued participation are explained to the participant and the reason for refusal is documented.

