7 SAFETY REPORTING

7.1 Reporting of Serious Adverse Events (including SUSARs)

No information for adverse events on specific drugs will be collected in this trial for the following reasons:

- Extensive safety data for evolocumab was already gathered in a rigorous, double-blind, placebo-controlled manner in a very large number of individuals in the FOURIER OUTCOMES trial.
- Amgen, the maker of evolocumab, is conducting two open-label extension studies of evolocumab in 6700 patients who received evolocumab in FOURIER OUTCOMES trial, thereby extending the duration of exposure to evolocumab to 7 years. (ClinicalTrials.gov Identifiers: NCT02867813 and NCT03080935).

Participants will be under the clinical care of their primary physician with no care provided by the NCC. If the investigator suspects or becomes aware of an adverse drug reaction(s) (serious or non-serious) or product complaints related to evolocumab use (past or current), this information shall be reported to Amgen within one (1) business day of the investigators' awareness or to the concerned competent authority via the national spontaneous reporting system. If it is not known what PCSK9i inhibitor a subject was on at the time of the event, this information will still be reported.

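### The PCSK9-inhibitor question in Appendix 1 rests on a premise that is false for the placebo arm and asks only about continued use, so post-trial use may be under-recorded, possibly unequally by arm

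*Protocol*

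**What the plan says.** Section 1 (Background) states: "The FOURIER OUTCOMES trial was a randomized double-blind placebo-controlled trial". It sets the comparison for this follow-up as "prior use of evolocumab compared with placebo during the randomized FOURIER OUTCOMES trial, irrespective of post-trial treatment with or without further evolocumab".

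Section 4.1 leaves post-trial treatment to participants and their physicians, "including any lipid-modifying medication (including PCSK9 inhibitors). Use of lipid-modifying therapy classes will be recorded". Section 5.2 says each participant will be asked for "lipid-lowering therapy classes used since the last contact" and points to Appendix 1 for the items. Section 6.6 defines the measurement as use of these classes during follow-up.

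Item (ix) in Appendix 1 asks: "Are you still taking a cholesterol lowering injection (PCSK9 inhibitor drug", and goes on "similar to as in the FOURIER trial (you needed to start one when you joined the FOURIER trial". The neighbouring item on absorption inhibitors is neutral: "Are you taking a medication (e.g., ezetimibe or Zetia) to slow absorption of cholesterol from your diet". Month and year are requested for the health events (i) to (vii), but not for the treatment items (viii) to (x).

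Section 7.1 mentions "two open-label extension studies of evolocumab in 6700 patients who received evolocumab in FOURIER OUTCOMES trial". The enrolment criteria in Sections 3.1 and 3.2 do not exclude these patients, and neither the schedule in Section 5.1 nor Appendix 1 records extension participation.

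**The concern.** The item has two faults. It tells former-placebo participants something untrue about their own treatment, and it asks a narrower question than Section 5.2 says is asked.

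The statin evidence in Section 1 is presented as persuasive partly because lipid-lowering use was nearly the same in the two original groups after those trials ended. A reader of this study will want the same reassurance about PCSK9 inhibitors. Item (ix) is the participant-reported source for it. If the item misses new starters or short-term users, the table of post-trial use by original arm will be wrong, and no analysis plan can recover data that were not collected.

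**Working it through.** No stated figure depends on item (ix), so the check is mainly textual: take the possible histories and see what a literal reader would answer.

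| History since last contact | Fits *still taking*? | Likely record | Used since last contact (Section 5.2)? |
|---|---|---|---|
| Former evolocumab, continued, taking it now | Yes | User | Yes |
| Former placebo, started after the trial, taking it now | No | May be non-user | Yes |
| Former evolocumab, stopped, later restarted, taking it now | Poorly | Uncertain | Yes |
| Either arm, started and stopped between contacts | No | Non-user | Yes |
| Either arm, never used | No | Non-user | No |

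1. **Interval use.** In the fourth row the literal answer is No, although Section 5.2 would count the person as a user. After the first year contacts are about a year apart (Section 5.1), so such use can go unseen. This follows from the wording alone.
2. **New starters.** In the second row neither the premise nor *still* fits. Some will answer Yes and some No, and the document does not let us say how many.
3. **Possible dependence on arm.** Every post-trial user from the placebo arm is a new starter. Users from the evolocumab arm can include continuers, as Section 7.1 shows. The wording therefore fits some users in one arm and none in the other.

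**Illustration only.** The document gives neither rates of use nor accuracy of answers, so all inputs here are assumed: equal true use *u* in both arms, no false Yes answers, and sensitivity of item (ix) of 0.95 in the former-evolocumab arm and 0.60 to 0.80 in the former-placebo arm.

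Recorded use = *u* × sensitivity.

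- *u* = 5%: 4.75% against 3.0 to 4.0%, a false difference of 0.75 to 1.75 points.
- *u* = 10%: 9.5% against 6.0 to 8.0%, a false difference of 1.5 to 3.5 points.
- *u* = 20%: 19% against 12 to 16%, a false difference of 3 to 7 points.

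If sensitivity is the same in both arms, the false difference is zero, though use is still under-recorded: 20% at a sensitivity of 0.80 is recorded as 16%.

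**The case against.** **The main comparison does not use the item.** Section 9.2 analyses events by original allocation, intention-to-treat, and Section 1 frames the hypothesis irrespective of further evolocumab. This stands. A reader might still infer that the treatment effect is biased by a calculable amount. For example, with no legacy effect and an assumed 20% on-treatment reduction, a difference *d* in the proportion using the drug gives a hazard ratio of about 1 − 0.2*d*: 0.98 at 10 points and 0.90 at 50. Those figures describe truly unequal use, for which the document gives no value. They would be the same however item (ix) were worded, so they do not measure this fault.

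**Misclassification by arm is not shown.** The parent trial was double-blind, and nothing in the protocol says participants learned their allocation. People unaware of their arm may read the item alike, and the error could be largely the same in both arms. This stands too: dependence on arm is a risk, not a finding.

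**There are other routes to the information.** Section 5.2 names treating doctors and, where permitted, registries. Section 3.2.2 keeps the FOURIER patient ID, which could support linkage. Repeated contacts can pick up a long-term user later. An Unsure answer leads to direct contact, although that instruction is printed before items (viii) to (x). So item (ix) cannot be called the only possible source. None of these routes reliably catches a confident but wrong No.

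**The extension studies prove little.** Section 7.1 cites them to explain why adverse events are not collected. The protocol does not say how many of the 6700 patients joined this study, so it does not support calling them the largest source of unequal exposure.

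**The exploratory use is itself stated in two ways.** The Synopsis speaks of the effect of using the classes. Section 2 speaks of effect modification by classes given at FOURIER entry, which would not need item (ix). The item still feeds Section 6.6 and the Synopsis objective.

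**Conclusion.** The point holds as a fault in data collection. The premise of item (ix) is false for the placebo arm, and the item does not collect what Section 5.2 says it collects. Post-trial starters may be recorded as non-users, and use that began and ended between contacts is lost if the item is answered literally. The error may differ by arm. That part rests on the assumption that new starters and continuers answer differently, which the protocol neither confirms nor excludes.

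The size cannot be computed from the document; the 0.75 to 7 points above are an assumption-based illustration. The intention-to-treat hazard ratios are untouched. The harm is to the description of PCSK9-inhibitor use by arm, to the Synopsis exploratory objective, and to the reading of any post-trial difference as a legacy effect rather than unequal continuing treatment. The item should be corrected, but the fault does not invalidate the primary analysis.

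**What to change.** Replace item (ix) with a neutral question that makes no reference to what was taken in FOURIER, for example: *Since we last had contact, have you taken a PCSK9-inhibitor injection (e.g. evolocumab)? Y/N/Unsure. If yes: are you taking it now? Month and year started and stopped? Was it through an extension study?*

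Ask items (viii) and (x) about use since last contact as well, so that all three match Section 5.2. The statin premise in (viii) is not in dispute; only the period asked about needs to change.

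The cost is one questionnaire amendment, with the ethics approval that Section 11.3 requires, and a slightly longer form. Section 12 shows the questionnaire has already been amended twice, including the response options of (viii) to (x). Answers already collected under the present wording cannot be repaired this way, so the form version should be kept with each answer.
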